## **5.5 Criteria for Temporary Discontinuation, Dose Reduction, and Resumption of Quizartinib**

- When the need arises to use drugs that may potentially prolong the QT/QTc interval or strong CYP3A4 inhibitors by necessity during the quizartinib treatment period: Quizartinib administration should be temporarily discontinued from the start to the end of use of the above-mentioned drugs. On the day when the quizartinib is resumed after interruption, vital sign measurement, 12-lead ECG, and laboratory tests will be performed before the start of quizartinib administration (refer to “6.2 Remission Induction Therapy” and “6.3 Consolidation Therapy”).
- When  $\geq$  Grade 3 QTcF prolongation occurs in a patient at Level 2: Quizartinib administration should be temporarily discontinued from the onset time of the above event.  
If the increase in QTcF recovers to  $\leq$  30 ms, compared with the value at registration, within 14 days after the onset, quizartinib administration will be resumed at a dose reduced to 20 mg/day.  
If the increase in QTcF does not recover to  $\leq$  30 ms, compared with the value at registration, within 14 days after the onset, the study for the relevant patient will be discontinued.  
\* If  $\geq$  Grade 3 QTcF prolongation occurs in a patient at Level 1, the study for the patient should be discontinued (refer to “5.6 Withdrawal Criteria”).
- When a DLT occurs (including cases in which it takes time to assess the causality with quizartinib, cytarabine, or the anthracycline drug but the toxicity can potentially be associated with quizartinib):  
If Grade 3 non-hematological toxicity (except QTcF prolongation) occurs during the induction phase and it is assessed to be “related” to quizartinib, quizartinib administration will be temporarily discontinued from the onset time of the event. If

the event resolves to Grade 1 within 28 days after the onset of the event and the investigator or subinvestigator decides it possible to resume quizartinib administration, quizartinib administration will be resumed.

If a Grade 4 non-hematological toxicity (except QTcF prolongation) occurs during the induction phase, the study for the relevant patient will be discontinued.

Once the dose of quizartinib is reduced, the dose should not be increased again to the original dose.

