### 4.2 Subject Withdrawal Criteria and Procedures

If a patient meets the criteria specified in "5.6 Withdrawal Criteria," the investigator or subinvestigator will withdraw the patient from study treatment and perform the examinations and assessments according to "6.4 At the Time of Withdrawal from the Study." The investigator or subinvestigator will record the date of withdrawal, reason for withdrawal, and examination/assessment results in the case report form (CRF).

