## **5.6 Withdrawal Criteria**

The study treatment must be withdrawn for any of the following reasons:

- 1) Overt disease progression
- 2) Intolerable AEs including the following:
  - Grade 4 non-hematological toxicity for which the relationship to the study drug is assessed as “related”
  - (For patients at Level 1) Grade 3 or higher QTcF prolongation or DLT
  - (For patients at Level 2) Any AE that does not lead to a situation allowing the resumption of study treatment, as specified in “5.5 Criteria for Temporary Discontinuation, Dose Reduction, and Resumption of Quizartinib.”
- 3) The need of the second dose reduction in patients with a dose reduction of the study drug
- 4) Achievement of CR, CRp, or CRi in Cycle 2 or later of consolidation therapy, leading to the decision of the investigator or subinvestigator to introduce HSCT
- 5) Patient’s withdrawal of consent for study participation
- 6) Ineligibility found after registration in the study
- 7) Patient found to be pregnant after registration in this study
- 8) Poor patient compliance with study procedures, including failure to visit the study center as scheduled in the protocol
- 9) Other circumstances why the study cannot be continued in the investigator’s or subinvestigator’s opinion

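### Sections 5.5 and 5.6 give opposite instructions for a related Grade 4 QTcF prolongation at Level 2 that recovers within 14 days: resume at 20 mg/day, or withdraw

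*Combined protocol and SAP*

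**What the plan says.** **Section 5.5, QTcF rule.** The trigger is "Grade 3 QTcF prolongation occurs in a patient at Level 2", with a greater-than-or-equal sign before the grade, so Grade 4 is included. Dosing stops at onset. If the increase over the registration value returns to 30 ms or less within 14 days, "quizartinib administration will be resumed at a dose reduced to 20 mg/day"; otherwise the patient's participation ends. The rule has no condition on causality, treatment phase or investigator judgement. A note sends Level 1 patients with the same event to discontinuation.

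**Section 5.5, Grade 4 rule.** "If a Grade 4 non-hematological toxicity (except QTcF prolongation) occurs during the induction phase, the study for the relevant patient will be discontinued". QTcF prolongation is carved out of this stop.

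**Section 5.6.** The list opens with "The study treatment must be withdrawn for any of the following reasons". Under intolerable adverse events it has three items:
- "Grade 4 non-hematological toxicity for which the relationship to the study drug is assessed as" related, with no limit by dose level, phase or type of event;
- for Level 1, QTcF prolongation of Grade 3 or higher, or a DLT;
- for Level 2, "Any AE that does not lead to a situation allowing the resumption of study treatment", with a reference to 5.5.

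Item 9 of the list adds a discretionary ground: "Other circumstances why the study cannot be continued in the" opinion of the investigator or subinvestigator.

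**Section 4.2.** When a criterion in 5.6 is met, "the investigator or subinvestigator will withdraw the patient from study treatment".

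**The concern.** QTc prolongation is the known cardiac risk of this drug, and the rule for stopping after it should give one answer. As written, one site could restart quizartinib after a related Grade 4 QTcF event and another could withdraw the patient, each following the protocol.

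The only Grade 4 QTc event described in the background (section 1.3.2) was torsades de pointes. A history of torsades excludes a patient at entry (section 4.1.2), and section 1.4 names it among the conditions on which quizartinib-induced torsades may depend. If such an event is graded as QTcF prolongation, 5.5 directs re-dosing of a patient who could no longer be enrolled.

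The safeguards are partial. Hospitalization (5.9) and renewed consent before resuming after a DLT (15.3) are tied to the DLT assessment period, which ends the day before consolidation Cycle 1 (5.4.1). The conflict has no phase limit. The extra ECGs on the day of resumption and on Days 4, 8, 11 and 15 (6.2, 6.3) are specified only after an interruption for QT-prolonging drugs or strong CYP3A4 inhibitors, not after a QTcF event.

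**Working it through.** The plan states no figure to reproduce. The check applies each rule to each possible case and then counts the dosing days that depend on the answer.

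**Rule comparison**

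| Case | 5.5 | 5.6 | Result |
|---|---|---|---|
| Level 1, Grade 3 or higher QTcF | Discontinue | Withdraw (Level 1 item) | Agree |
| Level 2, Grade 3, recovered in 14 days | Resume at 20 mg | No item met | Agree |
| Level 2, Grade 4, unrelated, recovered | Resume at 20 mg | Grade 4 item not met | Agree |
| Level 2, Grade 4, **related**, recovered | **Resume at 20 mg** | **Withdraw (Grade 4 item)** | **Conflict** |
| Level 2, Grade 3 or higher, not recovered | Discontinue | Withdraw (Level 2 item) | Agree |

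The discretionary item 9 is left out of the table because it applies equally to every row.

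**Does the 5.6 Grade 4 item cover QTcF at Level 2?** Three features of the text say yes.
1. 5.5 had to exempt QTcF prolongation from its own Grade 4 non-hematological rule, so the protocol counts it as a non-hematological toxicity. 5.6 has no such exemption.
2. The next two items in 5.6 are labelled by level and the Grade 4 item is not. Any one item is sufficient, so the Level 2 reference to 5.5 adds a ground for withdrawal and does not cancel another.
3. The Grade 4 rule in 5.5 is confined to induction. If the 5.6 item did not apply at Level 2, no explicit Grade 4 stop would cover a related Grade 4 toxicity other than QTcF at Level 2 in consolidation.

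**Dosing days at stake**

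Inputs (5.3.1): quizartinib on Days 8 to 21 of a 7+3 induction cycle, and on Days 6 to 19 of a 5+2 induction cycle or a consolidation cycle; up to 2 induction and 4 consolidation cycles.

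Days per course: 21 − 8 + 1 = 14, and 19 − 6 + 1 = 14.

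Ceiling on days at 20 mg/day in later courses if 5.5 is followed:

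| Onset | Formula | Days |
|---|---|---|
| Induction Cycle 1, Cycle 2 given | (1 + 4) × 14 | 70 |
| Induction Cycle 1, Cycle 2 skipped | 4 × 14 | 56 |
| Induction Cycle 2 | 4 × 14 | 56 |
| Consolidation Cycle 1 | (4 − 1) × 14 | 42 |
| Consolidation Cycle 2 | (4 − 2) × 14 | 28 |
| Consolidation Cycle 3 | (4 − 3) × 14 | 14 |
| Consolidation Cycle 4 | (4 − 4) × 14 | 0 |

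Days left in the current course would be extra. Under 5.6 the figure is 0 in every row.

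**Effect on dose finding.** A related non-hematological toxicity of Grade 3 or higher in induction is a DLT under 5.4.1, and QTcF prolongation is not among the exceptions. The event counts as a DLT whichever section is followed, so Table 5.4-2 gives the same decision.

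**The case against.** The strongest reply is that the intended rule can be inferred. 5.5 gives QTcF its own rule by dose level and removes it from both the Grade 3 and the Grade 4 general rules. 5.6 names QTcF only in the Level 1 item and refers Level 2 patients to 5.5. On that reading, the Grade 4 item in 5.6 is the counterpart of the general rule in 5.5 with its exception left out by oversight, and re-challenge at 20 mg was meant. This is plausible as a guess at intent. It does not remove the conflict: the withdrawal rule is mandatory, has no exception, and cannot be confined to Level 1 without leaving the consolidation gap shown above.

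Several other points stand:
- Section 4.2 only refers to 5.6. It confirms that withdrawal follows but sets no separate criterion.
- The torsades case occurred at 90 mg/day with a strong CYP3A4 inhibitor. Here the maximum is 40 mg, and quizartinib is interrupted while such drugs are used.
- In Table 1.3-1, QTcF above 500 ms occurred in 5% of 38 patients at 30 mg and 3% of 36 at 60 mg, in a row labelled Grade 3 and asymptomatic.
- If torsades were recorded as an event in its own right, the QTcF exception might not reach it and both sections would stop treatment in induction. The documents do not say how it would be recorded, and section 1.3.2 labels it QTc prolongation.
- Item 9 of 5.6 lets the investigator withdraw the patient in any phase. That allows a safe choice but does not withdraw the instruction to resume.
- The day counts are ceilings on exposure, not measures of harm.

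**Conclusion.** The plan is wrong as written, within narrow limits. For a related Grade 4 QTcF prolongation at Level 2 that recovers within 14 days, 5.5 requires resumption and 5.6 requires withdrawal, with no order of precedence. Adjacent cases are consistent.

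The consequence is for patient safety and consistent conduct. The number exposed is small: normally 3 to 6 patients at Level 2 under Table 5.4-2, and the event is expected to be rare. No probability is claimed, because the documents give no Grade 4 rate in the relevant dose range. The 70-day ceiling assumes onset in induction Cycle 1, recovery within 14 days, renewed consent, 5% or more myeloblasts on Day 21 so that induction Cycle 2 is given, and all four consolidation cycles with no second event and no transplant. Dose escalation, MTD determination and sample size are unaffected; at most, discontinuation counts in descriptive tables would differ.

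The point should be fixed because it concerns a stopping rule for a potentially lethal toxicity and the repair is short.

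**What to change.** Unless re-challenge after Grade 4 is intended, amend 5.5:
1. Keep the immediate interruption for any QTcF prolongation of Grade 3 or higher at Level 2.
2. Allow resumption at 20 mg/day only for Grade 3 events, or Grade 4 events assessed as unrelated. Keep dosing on hold after a Grade 4 event until causality has been assessed.
3. State that a related Grade 4 QTcF prolongation, in any phase, leads to withdrawal under 5.6.
4. In the Grade 4 stopping rule, replace the QTcF exception with a reference to the QTcF rule.

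If the sponsor does intend re-challenge at 20 mg/day after a related Grade 4 event, leave 5.5 as it is and add one exception, for QTcF prolongation at Level 2, to the Grade 4 item in 5.6. The choice is clinical. Withdrawal is the safer default when the documents do not settle it.

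Either route costs a wording amendment. Under 15.7, a new protocol version needs the investigator's written agreement and the study center's own procedures. Sample size, visits and analyses do not change.

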Assessment of bone marrow findings (antitumor effect)											The day ●	
HIV antibody tests												
Central measurement	Pharmacokinetics											
	FLT3-ITD and c-KIT mutations											
	Phosphorylated protein levels in blood, including FLT3											
	Inhibitory activity of plasma quizartinib on phosphorylated FLT3 protein											
Assessment of concomitant drugs and therapies												
Monitoring of AEs												

- Mandatory, ○ To be performed only in selected patients

- a) Before the start of administration of cytarabine and the anthracycline drug
- b) Pre-dose, 2 hours ( $\pm 10$  minutes) post-dose, 4 hours ( $\pm 10$  minutes) post-dose, and 6 hours ( $\pm 10$  minutes) post-dose
- c) Pre-dose, 2 hours ( $\pm 10$  minutes) post-dose, and 4 hours ( $\pm 10$  minutes) post-dose
- d) Pre-dose, 30 minutes ( $\pm 10$  minutes) post-dose, 1 hour ( $\pm 10$  minutes) post-dose, 2 hours ( $\pm 10$  minutes) post-dose, 4 hours ( $\pm 10$  minutes) post-dose, and 6 hours ( $\pm 10$  minutes) post-dose
- e) -3 days to the day

\* Remission induction therapy in Cycle 2 will be given using the same regimen as in Cycle 1 ("7 + 3") or on the dosing schedule ("5 + 2") shown in the table.

\*\*If drugs that may potentially prolong the QT/QTc interval or strong CYP3A4 inhibitors are used after the start of quizartinib treatment, quizartinib treatment should be interrupted from the start to the end of use of these drugs.

After the day when quizartinib is resumed, the following procedures will be performed at the time points listed below:

[1] Pre-dose of quizartinib on the day when the drug is resumed:	Vital sign measurement, 12-lead ECG, and laboratory tests
[2] 2 hours ( $\pm 10$ minutes) post-dose of quizartinib on the day when the drug is resumed:	Vital sign measurement and 12-lead ECG
[3] Pre-dose of quizartinib on Day 4 ( $\pm 1$ day) when defining the day when the drug is resumed as Day 1:	Vital sign measurement and 12-lead ECG
[4] Pre-dose of quizartinib on Day 8 ( $\pm 1$ day) when defining the day when the drug is resumed as Day 1:	Vital sign measurement and 12-lead ECG
[5] Pre-dose of quizartinib on Day 11 ( $\pm 1$ day) when defining the day when the drug is resumed as Day 1:	Vital sign measurement and 12-lead ECG
[6] Pre-dose of quizartinib on Day 15 ( $\pm 1$ day) when defining the day when the drug is resumed as Day 1:	Vital sign measurement and 12-lead ECG

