Study 2689-CL-2004 was conducted in 76 FLT3-ITD positive AML patients, who were assigned to 28-day cycles of 30 or 60 mg/day continuous dosing of quizartinib (for both males and females) to evaluate the efficacy and safety of quizartinib at lower doses than those tested in Study AC220-002. In the study, the incidence of QTc prolongation was much lower than that observed in Study AC220-002, indicating that the risk of QTc prolongation was dose-dependent (Table 1.3-1). The study also demonstrated that the CRc rates were comparable to those observed in Study AC220-002 (Table 1.3-2). In Study 2689-CL-2004 as well, 34% of patients proceeded to HSCT, and the patients who underwent HSCT tended to have a longer survival than those who did not.

Common adverse events (AEs) reported in Studies AC220-002 and 2689-CL-2004 were gastrointestinal disorders (eg, nausea, diarrhea, and vomiting), hematotoxicities (eg, anemia, neutropenia, and thrombocytopenia), febrile neutropenia, fever, fatigue, and QTc prolongation. Although the hematologic toxicities appear to be associated with the underlying disease, AML, data suggest delayed recovery or continued suppression of absolute neutrophil count (ANC) and platelets as a consequence of continued treatment with quizartinib.

Table 1.3-1 Maximum Values of QT Corrected for Heart Rate Using Fridericia's Method (QTcF) and Maximum Changes from Baseline in QTcF in Two Phase 2 Studies

Daily Dose of Quizartinib	Study AC220-002			Study 2689-CL-2004	
	90 mg/day (N = 57) † Female	135 mg/day (N = 67) † Male	200 mg/day (N = 12)	30 mg/day (N = 38)	60 mg/day (N = 36)*
Maximum QTcF (ms)					
> 480, ≤ 500 (Grade 2)	21%	13%	33%	5%	14%
> 500 (Grade 3) † Asymptomatic	21%	15%	42%	5%	3%
Maximum change in QTcF from baseline (ms)					
≤ 30	9%	9%	0%	50%	44%
> 30, ≤ 60	46%	51%	8%	47%	36%
> 60	46%	39%	92%	3%	19%

\* Two patients in the 60 mg/day group were randomized but never treated with quizartinib.

Table 1.3-2 Composite Complete Remission and Partial Response Rates in Two Phase 2 Studies

Daily Dose of Quizartinib	Study AC220-002			Study 2689-CL-2004	
	90 mg/day (N = 57) † Female	135 mg/day (N = 67) † Male	200 mg/day (N = 12)	30 mg/day (N = 38)	60 mg/day (N = 38)
CRc rate	47%	45%	42%	47%	47%
PR rate	25%	28%	50%	13%	24%

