### **1.3.4 Pharmacokinetics**

Pharmacokinetic data of quizartinib and its active metabolite AC886 from clinical studies in AML patients and healthy volunteers have been evaluated. After administration of quizartinib, the plasma concentrations of quizartinib and AC886 increased rapidly (Tmax of quizartinib, 2 to 8 hours post quizartinib dosing during the first day of dosing). Quizartinib and AC886 had terminal elimination half-lives of approximately 3 days, resulting in approximately 4-fold accumulation from the first day of dosing for exposure at the steady state after daily dosing. Plasma exposure to both quizartinib and AC886 was generally proportional with the dose in the tested dose range of 30 mg/day to 90 mg/day. Overall, Cmax and AUC showed moderate to high variability. Plasma concentrations of AC886 at the steady state paralleled quizartinib levels with a plasma concentration ratio of AC886 to quizartinib (AC886/quizartinib) of 0.5. AC886 is the only major metabolite of quizartinib in the circulation. Quizartinib was mainly eliminated by non-renal clearance. The presence of concomitant ketoconazole, a strong CYP3A4 inhibitor, increased the observed AUCinf of quizartinib approximately 2-fold. The presence of concomitant fluconazole, a moderate CYP3A4 inhibitor, increased the observed AUCinf of quizartinib approximately 1.2-fold.

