#### **4.1.2 Exclusion Criteria**

- 1) Diagnosis of acute promyelocytic leukemia
- 2) Chronic myeloid leukemia in blast crisis (patients with BCR-ABL [breakpoint cluster region- c-Abelson] fusion gene)
- 3) Diagnosis of treatment-related myeloid tumor
- 4) Having received other investigational products or having used any investigational medical devices within 30 days before registration in the study.
- 5) History of malignant tumor except for the following
  - Adequately treated non-melanoma skin cancer
  - Curatively treated mucosal carcinoma or carcinoma in situ with no evidence of relapse for  $\geq$  2 years after the local treatment
- 6) History of or current cardiovascular disease as specified below:
  - Heart rate  $<$  50 beats/min, determined as the average of three measurements taken along with 12-lead ECG within 14 days before registration in the study (excluding patients having a cardiac pacemaker)
  - QT corrected for heart rate using Fridericia's method (QTcF) of  $\geq$  450 ms, determined as the average of three measurements taken within 14 days before registration in the study
  - Diagnosed or suspected congenital long QT syndrome
  - Systolic blood pressure level  $\geq$  180 mmHg or diastolic blood pressure level  $\geq$  110 mmHg within 7 days before registration in the study
  - History of clinically significant ventricular arrhythmia (ventricular tachycardia, ventricular fibrillation, TdP, etc.)
  - History of Mobitz II atrioventricular block or third degree atrioventricular block (Patients who have a cardiac pacemaker but have not experienced syncope or clinically significant arrhythmia during the period of use are allowed to take part in the study.)
  - History of uncontrolled angina pectoris or myocardial infarction within 6 months before registration in the study
  - History of Class 3 or more severe heart failure according to "Appendix 2 New

York Heart Association (NYHA) Functional Classification”

- History of left ventricular ejection fraction below 45% or the lower limit of the institutional reference range, whichever is lower
- Complete left or right bundle branch block

7) Acute and active infection uncontrolled by antibacterial or antiviral agents or chronic and systemic infection

8) Active and clinically significant liver disease (hepatitis B, hepatitis C, etc.)

9) Tested positive for human immunodeficiency virus (HIV) antibody within 14 days before registration in the study

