### **5.9 Management of Patients**

The investigator or subinvestigator will strive to ensure the maximum safety of patients throughout the study period. Patients must be hospitalized during the DLT assessment period (refer to “5.4.1 Definition of Dose-limiting Toxicities”). Patients will be allowed to make a temporary overnight stay outside the hospital during the hospitalization period if the investigator or subinvestigator considers it possible after careful examination of the patient. If a patient makes an overnight stay outside the hospital, the study staff at the study center will instruct the patient how to contact the study center in the event of an emergency, prior to making an overnight stay outside the hospital.

If an AE occurring during hospitalization does not resolve or is not relieved until the planned day of discharge, the investigator or subinvestigator will decide the need to continue hospitalization or not in consideration of patient safety assurance.

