	Day 28 (-3 days to the day)	—

In patients who use drugs that may potentially prolong the QT/QTc interval or strong CYP3A4 inhibitors, 12-lead ECG will be measured at the following time points: [1] pre-dose of quizartinib on the following day of the end of use of the drugs (ie, the

day when quizartinib is resumed); [2] 2 hours ( $\pm$ 10 minutes) post-dose on the day when quizartinib is resumed; [3] pre-dose on Day 4 ( $\pm$ 1 day) if the day when quizartinib is resumed is defined as Day 1; [4] pre-dose on Day 8 ( $\pm$ 1 day) if the day when quizartinib is resumed is defined as Day 1; [5] pre-dose on Day 11 ( $\pm$ 1 day) if the day when quizartinib is resumed is defined as Day 1; and [6] pre-dose on Day 15 ( $\pm$ 1 day) if the day when quizartinib is resumed is defined as Day 1.

6) Laboratory tests

Cycle 1  * In case of “7 + 3”	Day 1	Before the start of administration of cytarabine and the anthracycline drug
	Day 8  * First day of quizartinib administration	Before administration of quizartinib
	Day 15	Before administration of quizartinib
	Day 21  * Last day of quizartinib administration	Before administration of quizartinib
	Day 28 ( $-3$ days to the day)	—
Cycle 2  * In case of “5 + 2”	Day 1	Before the start of administration of cytarabine and the anthracycline drug
	Day 8  * First day of quizartinib administration	Before administration of quizartinib
	Day 15	Before administration of quizartinib
	Day 21  * Last day of quizartinib administration	Before administration of quizartinib
	Day 28 ( $-3$ days to the day)	—
Cycle 2  * In case of “5 + 2”	Day 1	Before the start of administration of cytarabine and the anthracycline drug
	Day 6  * First day of quizartinib administration	Before administration of quizartinib
	Day 15	Before administration of quizartinib
	Day 19  * Last day of quizartinib administration	Before administration of quizartinib
	Day 28 ( $-3$ days to the day)	—

In patients who use drugs that may potentially prolong the QT/QTc interval or strong CYP3A4 inhibitors, laboratory tests will be performed pre-dose of quizartinib on the following day of the end of use of the drugs (ie, the day when quizartinib is resumed).

7) Assessment of antitumor effect

Bone marrow findings and neutrophil and platelet counts in the peripheral blood will be assessed as specified in “10.1 Definition of Efficacy Endpoints.”

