### **15.3 Procedures for Informed Consent**

The investigator or subinvestigator will explain the details of the study listed below to subject candidates in a readily understandable way using the informed consent documents, before any invasive procedures related to the study are performed in each subject, and obtain written informed consent to participate in the study by their free will. Before obtaining consent, the investigator or subinvestigator should give the subject

candidates ample time and opportunity to ask questions to decide whether to participate in the study, and should answer the questions in an appropriate manner.

Before the start of study drug administration in Cycle 1 of consolidation therapy, written informed consent to continue participation in the study after the end of the DLT assessment period will be obtained again from the subjects. For subjects who experienced any DLTs during the DLT assessment period, written informed consent to continue participation in the study will be obtained again before resuming the study drug administration after recovery from the toxicity.

The investigator or subinvestigator who has provided an explanation and the subject who has given consent will sign and date the consent form. If study staff personnel provide a supplementary explanation to the subject candidates, the study staff should sign and date the form. The investigator or subinvestigator will provide a copy of the consent form along with the subject information form to the subject, and retain the original consent form at the study center. The investigator or subinvestigator will document (eg, in the original consent form or medical record) that a copy of the consent form and subject information form have been provided to the subject.

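### A Level 2 patient restarted at 20 mg/day after Grade 3 or higher QTcF prolongation has no ECG or laboratory checks tied to the restart; the protocol's resumption checks apply only after an interacting-drug hold

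*Combined protocol and SAP*

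**What the plan says.** Protocol section 5.5 treats two kinds of hold in separate bullets.

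- **Interacting-drug hold.** Quizartinib stops while a QT-prolonging drug or strong CYP3A4 inhibitor is in use. Vital signs, 12-lead ECG and laboratory tests precede the first resumed dose, and the bullet refers to 6.2 and 6.3 for the rest. Section 6.2 sets the trigger for ECGs as follows: "In patients who use drugs that may potentially prolong the QT/QTc interval or strong CYP3A4 inhibitors, 12-lead ECG will be measured at" the listed points, which are pre-dose and 2 hours on the resumption day, then pre-dose on resumption Days 4, 8, 11 and 15 (each ±1 day). The vital-sign and laboratory items of 6.2, and all three items in 6.3, carry the same trigger. So do the footnotes to the synopsis schedules and to Tables 6-1 and 6-2, which begin "If drugs that may potentially prolong the QT/QTc interval or strong CYP3A4 inhibitors are used after the start of quizartinib treatment".
- **QTcF hold at Level 2.** Quizartinib stops at onset of Grade 3 or higher QTcF prolongation. If the increase over the registration value is 30 ms or less within 14 days, "quizartinib administration will be resumed at a dose reduced to 20 mg/day"; otherwise the patient stops the study. No tests are named and there is no cross-reference to 6.2 or 6.3.

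**The concern.** Section 1.4 lists preexisting QTc prolongation, hypokalemia and hypomagnesemia among the conditions that can lead to torsades de pointes. A patient who has had QTcF above 500 ms and is given the drug again is the patient for whom an ECG and electrolytes at restart matter most. By rule, that patient has fewer restart checks than one whose hold was a precaution. Table 1.3-1 marks the > 500 ms category as asymptomatic, so clinical observation without an ECG could miss a recurrence. A missed recurrence also matters for management, because section 5.6 withdraws a patient who needs a second dose reduction.

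**Working it through.** The protocol states no figure to reproduce. The check counts what the routine calendar provides after a QTcF restart.

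**Inputs**

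- Routine ECG days during dosing (6.2, 6.3): induction Cycle 1, Days 8, 9, 15, 21; Cycle 2 in the 7 + 3 regimen, Days 8, 15, 21; Cycle 2 in the 5 + 2 regimen, Days 6, 15, 19; consolidation, Days 6, 13, 19. Laboratory days are the same except Day 9.
- Dosing windows: Days 8–21, or Days 6–19 in 5 + 2 and consolidation.
- Half-life (1.3.4): "Quizartinib and AC886 had terminal elimination half-lives of approximately 3 days, resulting in approximately 4-fold accumulation from the first day of dosing".
- Entry limit (4.1.2): QTcF of 450 ms or more is excluded, "determined as the average of three measurements taken within 14 days before registration in the study". Grade 3 is above 500 ms (Table 1.3-1), so the rise over registration exceeds 50 ms.

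**Time to recover to 30 ms.** Assume the QTcF rise is proportional to concentration. Then time = 3 × log2(rise / 30) days:

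- 50 ms: 2.2 days
- 60 ms: 3.0 days
- 80 ms: 4.2 days
- 100 ms: 5.2 days

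**Same-cycle restart, event found at the mid-window ECG** (Day 15, or Day 13 in consolidation). Possible restart days run from onset plus recovery time to the last dosing day. They are summed over induction Cycle 1, 7 + 3, 5 + 2, consolidation Cycle 1, and consolidation Cycle 2 onward.

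| Minimum recovery | Possible restart days | No routine ECG or laboratory tests that day | Longest wait for next ECG |
|---|---|---|---|
| 2 days | 5+5+3+5+5 = 23 | 18 | 4 days |
| 3 days | 4+4+2+4+4 = 18 | 13 | 3 days |
| 5 days | 2+2+0+2+2 = 8 | 4 | 1 day |

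Example: a restart on Day 18 of induction Cycle 1 has no routine test that day. The next ECG, on Day 21, is resumption Day 4. What is missing is mainly the restart-day check.

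**Same-cycle restart, event found at the first-dose ECG**, with restart 3 to 6 days later: the wait is up to 4 days, or 6 in 5 + 2 (restart Day 9, next ECG Day 15).

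**Next-cycle restart on the first dosing day.** A pre-dose ECG and laboratory tests are already scheduled. The next ECG is 15 − 8 = 7 days later in 7 + 3, 13 − 6 = 7 in consolidation, and 15 − 6 = 9 in 5 + 2. Nothing falls near resumption Days 4 and 11 (Days 4 and 8 in 5 + 2). With a 3-day half-life, exposure from the resumed doses is 1 − 2^(−4/3) = 60% of steady state after 4 doses and 1 − 2^(−8/3) = 84% after 8, so it is still rising across that gap.

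**How many patients.** Table 1.3-1 gives QTcF above 500 ms in 5% at 30 mg and 3% at 60 mg, in patients "who were assigned to 28-day cycles of 30 or 60 mg/day continuous dosing of quizartinib". If 3–5% held at 40 mg for 14 days with chemotherapy, the chance of at least one Grade 3 event at Level 2 would be:

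- 3 patients: 1 − 0.97³ = 9% to 1 − 0.95³ = 14%
- 6 patients: 1 − 0.97⁶ = 17% to 1 − 0.95⁶ = 26%

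The expected number of events is 3 × 0.03 = 0.09 to 6 × 0.05 = 0.30. Restarts would be fewer, since patients who do not recover in 14 days, or who have a related Grade 4 event, do not restart.

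**The case against.** The QTcF restart is not uncontrolled.

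- It is the only restart with a QTcF criterion, which cannot be met without an ECG.
- The dose is reduced for good, and a need for a second reduction means withdrawal (5.6). After an interacting drug, by contrast, quizartinib normally resumes the next day at full dose with no QTcF threshold (5.7), which can justify a different schedule.
- In induction, "Patients must be hospitalized during the DLT assessment period" (5.9). If the event was a DLT, "written informed consent to continue participation in the study will be obtained again before resuming the study drug administration after recovery from the toxicity" (15.3).
- Section 9.5.1 requires adverse events to be followed until recovery as far as possible.
- A restart in consolidation Cycle 1 already has eight routine ECG time points (four on Day 6, three on Day 13, one on Day 19), against six in the special schedule.

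All of this stands, and it rules out the reading that such a patient has no check at restart. The 30 ms condition and the same-day routine tests in a next-cycle restart contradict that reading. What remains is that none of these provisions sets the timing of an ECG or electrolytes relative to the restart. The recovery ECG also precedes renewed exposure, and hospitalization is required only during the DLT period, not in consolidation.

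A reader might also take 13 of 18 as the chance of an unchecked restart. It is an unweighted count of calendar days that rests on assumed detection and recovery times. With 5-day recovery it becomes 4 of 8, each with an ECG the next day. If the event is found on the last dosing day, no same-cycle restart is possible.

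Finally, the footnote sentence introducing the resumption time points could look general if read alone. It sits under the interacting-drug condition, which 6.2 and 6.3 repeat explicitly.

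**Conclusion.** The gap is real and modest. After a QTcF hold at Level 2, the protocol mandates no ECG, vital signs or laboratory tests tied to the restart beyond the routine calendar. In a same-cycle restart the next routine ECG is typically 0 to 3 days away, assuming mid-window detection and at least 3 days to recover. The wait is up to 4 days with 2-day recovery or early onset, and up to 6 with early onset in 5 + 2. In a next-cycle restart the first dosing day is covered and the following ECG is 7 days later, or 9 in 5 + 2. The patient numbers are small and rest on rates borrowed from continuous dosing at other doses.

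A reader might infer that the MTD is put at risk. The documents do not support that: a related Grade 3 QTcF event in induction already meets the DLT definition in 5.4.1, and a consolidation event falls outside the DLT period. This is a patient-safety improvement worth making because it is cheap. Investigators may well do these tests anyway, but the protocol does not require them.

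**What to change.** Add one sentence to the QTcF bullet of 5.5:

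> Where resumption is permitted, vital signs, 12-lead ECG and laboratory tests will be performed before the first resumed dose, and vital signs and 12-lead ECG at 2 hours post-dose and pre-dose on Days 4, 8, 11 and 15 (±1 day) counted from the day of resumption, while dosing continues.

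Add a cross-reference to it in 6.2, 6.3 and the schedule footnotes. Extending the trigger inside the existing interacting-drug sentences would not work. Those sentences fix the first time point to the day after the other drug ends, and the footnotes define the hold by that drug's use; neither exists in a QTcF hold. The opening words of the new sentence keep the 5.6 withdrawal of related Grade 4 events intact. The reduced dose and the 30 ms condition do not change.

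Extra ECG and vital-sign time points per restart:

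- Same-cycle after mid-window onset with at least 3 days to recover: 2 on the 13 restart days without a routine ECG, and 0 or 1 on the other 5.
- Next-cycle: 2, or 3 from consolidation Cycle 2, where the routine first-day ECG is pre-dose only.
- Same-cycle after early onset: 2 to 4.

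There is at most one extra laboratory set per restart, and none for a next-cycle restart. While dosing continues, planned ECGs after a restart would then be at most 4 days apart (6 with the ±1 day windows).
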